Ablation Targets of Scar-related Ventricular Tachycardia Identified by Dynamic Functional Substrate Mapping

Registration number: NCT05086510

Date: 28th September 2021

Methods

Patients

Consecutive patients presenting to Ain Shams University hospitals for ablation of ventricular tachycardia were evaluated for participation in the study. Patient recruitment period was from October 2021 till January 2023. Approval was obtained from the ethical committee at Ain shams University before starting the research.

- ***Inclusion criteria***

- Patients with structural heart disease including previous myocardial infarction, left ventricular (LV) dilatation and/or systolic dysfunction, or normal LV diameters and systolic function with evidence of ventricular scar on contrast enhanced-cardiac magnetic resonance (ce-CMR) or electroanatomic map (EAM).
- Sustained monomorphic VT documented by 12-lead electrocardiogram (ECG) or implantable cardioverter defibrillator (ICD) electrograms resistant to antiarrhythmic drug treatment or requiring ICD therapies.

- ***Exclusion criteria***

- Patients with ventricular arrhythmias attributed to reversible causes.

Methods:

On admission, patients were subjected to the following after a written informed consent:

A. History taking:

1. Age & sex.
2. Smoking status.
3. Medical history including hypertension (HTN), diabetes mellitus (DM), renal

impairment, etc.

4. Previous history of coronary artery disease, myocardial infarctions (MI), revascularization procedures
5. Previous episodes of ventricular tachycardia, requirement for external shock, ICD shocks.
6. Medical treatment with special emphasis on antiarrhythmic drugs.

B. Physical examination: with special emphasis on vital data including general & local examination.

C. 12 lead surface ECG: during sinus rhythm and of VT(s); if available.

D. Laboratory investigations: Including serum electrolytes, kidney function

E. Echocardiography will be done routinely for all patients with special emphasis on ejection fraction (to be assessed by Simpson's method), left ventricular dimensions, resting segmental wall motion abnormalities (RSWMAs).

F. Coronary angiography according to the patient's clinical characteristics; if there is doubt about coronary artery disease as contributor to VT or LV dysfunction.

G. Randomization:

Patients were randomly allocated to either DEEP group or non-DEEP group before the procedure. Patients were informed of the group to which they have been randomized.

H. Procedure:

The electrophysiological study and ablation was conducted under general anesthesia under supervision of an anesthesiologist. Continuous Non-invasive or intra-arterial blood pressure monitoring and digital pulse oximetry were performed. ICD therapies were inactivated.

Vascular sheaths were inserted into the right femoral vein (2 to 3), right femoral artery and/or subxiphoid area under local anesthesia (bupivacaine). A steerable quadripolar or decapolar catheter was positioned in the right ventricular apex or coronary sinus. The access was via endocardial retroaortic approach, trans-septal approach, epicardial approach or endocardial retroaortic with ad-hoc epicardial approach. Epicardial mapping and ablation was performed when preprocedural ce-

CMR showed epicardial scar, endocardial mapping did not identify subendocardial scars, unipolar LV mapping suggested the presence of epicardial scar, ECG of clinical or induced VT suggests epicardial origin (Berruezo *et al.*, 2004) (Vallès, Bazan and Marchlinski, 2010). The right ventricle (RV) was mapped when right ventricular origin of VT was suspected e.g. in arrhythmogenic right ventricular cardiomyopathy (ARVC). Surface electrocardiograms (ECGs) and bipolar intracardiac electrograms were continuously monitored.

I. Mapping and Ablation Strategy:

All patients underwent bipolar voltage mapping during sinus rhythm. Mapping was performed by either an irrigated tip ablation catheter (ThermoCool SF™ catheter; Biosense Webster, Diamond Bar, CA, USA), (ThermoCool ST™ catheter; Biosense Webster, Diamond Bar, CA, USA), (FlexAbility™; Abbott, St. Paul, MN, USA), (TactiCath™; Abbott, St. Paul, MN, USA) or a multi-electrode mapping catheter (Pentaray™, Biosense Webster, Diamond Bar, CA, USA). Late potentials (LPs) (defined as sharp high frequency or fractionated potentials at or after the terminal portion of QRS (Arenal *et al.*, 2003)) were pinpointed and tagged.

Patients allocated to the DEEP group were subjected to further analysis of their LPs by RV extrastimulus pacing. This constituted an S1 drive train at 600 ms or 500 ms (according to the sinus rhythm cycle length) followed by a single S2 extrastimulus at 20 ms longer than the ventricular effective refractory period. Thereafter, the time interval from the surface ventricular far-field signal to the local bipolar LP electrogram was measured both during the RV drive train and with S2 extrastimulus. If the difference between the 2 measured values was > 10 ms, the analyzed LP was annotated as a DEEP. The same applied for multicomponent signals where DEEP was annotated if there was a more than 10 ms splitting of components in response to S2 (Figure 1) (Porta-Sánchez *et al.*, 2018). The percentage of points with LPs and DEEPs was calculated in relation to the total number of mapped points.

Figure (1): Intracardiac electrogram demonstrating DEEP

Figure (1): Intracardiac electrogram of a patient with arrhythmogenic right ventricular cardiomyopathy during right ventricular S1-S2 pacing. The late component of the paced QRS on the distal pole of ablation catheter shows significant delay with extrastimulation denoting a DEEP

Ablation was performed by ThermoCool SF™ catheter (Biosense Webster), ThermoCool ST™ catheter (Biosense Webster), FlexAbility™ (Abbott) or TactiCath™ (Abbott). Concerning the DEEP group, ablation was initially restricted to points with DEEPs, while in the non-DEEP group, ablation aimed at elimination of all LPs. Acute success was defined as VT non-inducibility, including both clinical and non-clinical tachycardias. If VT was still inducible after ablation, activation and entrainment mapping were performed for hemodynamically-tolerated tachycardias, aiming at identification of the critical components of the re-entrant circuit -according to previously defined criteria (Brunckhorst *et al.*, 2004)(Stevenson *et al.*, 1997),

followed by ablation at such locations. If the VT was untolerated, pacemapping was performed aiming at a $> 96\%$ match (Bogun *et al.*, 2006).

J. Follow up:

The study population was followed up for a mean duration of 12 months for the occurrence of the study endpoints. The primary endpoint was VT recurrence rates. Secondary endpoints were all-cause mortality and cardiovascular mortality. For patients with implanted defibrillators, follow up was done by interrogation of device recordings, while when defibrillators were not implanted, follow up was by history taking for the occurrence of symptoms or need for emergency department admission attributed to recurrence of VT.

K. Statistical analysis:

Continuous variables with normal distribution are presented as mean \pm standard deviation and range whilst those with non-normal distribution are reported as median and interquartile range (IQR). Continuous variables were compared by Student's t-test, while categorical variables were compared by chi-square tests, or Fisher's exact tests as appropriate. Statistical analysis were performed using SPSS 25 for Windows (SPSS Inc, Chicago, Illinois, USA).

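### VT recurrence would be compared without adjustment in a clinically mixed population; pre-naming LVEF and ischaemic status as covariates would correct for chance imbalance in them and gain modest precision

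*Combined protocol and SAP*

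**What the plan says.** - **Population (Inclusion criteria).** Eligible are "Patients with structural heart disease including previous myocardial infarction, left ventricular (LV) dilatation and/or systolic dysfunction, or normal LV diameters and systolic function", the last group provided that scar is shown on CMR or on the electroanatomic map. Sections H and I also provide for ARVC: as a reason to map the right ventricle, and in the Figure 1 legend.
- **Allocation (section G).** "Patients were randomly allocated to either DEEP group or non-DEEP group before the procedure". No ratio, blocking, stratification or minimisation is given.
- **Baseline data (on-admission items, listed ahead of G).** Item E: "Echocardiography will be done routinely for all patients with special emphasis on ejection fraction", by Simpson's method. Item A4: "Previous history of coronary artery disease, myocardial infarctions (MI), revascularization procedures". Item F makes angiography selective: "Coronary angiography according to the patient's clinical characteristics; if there is doubt about coronary artery disease as contributor to VT or LV dysfunction".
- **Endpoint and analysis (sections J and K).** "The primary endpoint was VT recurrence rates". Section K says "categorical variables were compared by chi-square tests" or Fisher's exact test, with Student's t-test for continuous variables. It has no regression, stratified test or covariate list, and does not say which test serves the primary endpoint.

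**The concern.** Neither the design nor the analysis uses baseline prognosis. If patients with different heart disease or different LVEF recur at different rates, and the arms happen to differ in that mix, the difference in mix is carried into the observed recurrence difference. None of the listed methods can remove it. Prognostic data that are already measured also go unused, so the comparison is less precise than it could be. Finally, with no covariates named in advance, any adjustment made after an imbalance has been seen is open to challenge as data-driven.

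**Working it through.** The plan has no figure to reproduce: it states no sample size, alpha, event rate, aetiology split or prognostic effect. Everything below is an illustration.

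**Assumptions**
- 20, 30 or 50 per arm, equal arms, simple allocation. One centre recruiting from October 2021 to January 2023, about 16 months, suggests a small trial but does not establish one.
- Aetiology split 60/40. Recurrence is 26% in the larger group and 50% in the smaller. For the shift in step 2, a rounded gap of 25 points is used, with range 15-35.
- LVEF effect: log-odds 0.6 per SD. Two-sided 5% level.

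**1. Chance of imbalance.** The SD of the between-arm difference in aetiology share is √(2 × 0.6 × 0.4 / n), which is 15.5, 12.6 and 9.8 points at n = 20, 30 and 50. The exact binomial chance of a difference of 15 points or more is 42.0%, 23.5% and 12.5%. As a sensitivity check with other inputs (factor prevalence 30-50%, exact hypergeometric), the chance of 20 points or more is about 30-34% at 40 patients in total, 16-20% at 60, 5-7% at 100 and under 1% at 200.

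**2. Shift in the estimate.** Shift = imbalance × risk gap.
- 0.15 × 25 = 3.75 points (0.15 × 15 = 2.25; 0.15 × 35 = 5.25).
- Overall recurrence is 0.6 × 26% + 0.4 × 50% = 35.6%.
- The crude SE is √(2 × 0.356 × 0.644 / n), which is 0.151, 0.124 and 0.096 at n = 20, 30 and 50.
- At 30 per arm the shift is 3.75 / 12.4 = 0.30 SE (range 2.25 / 12.4 = 0.18 to 5.25 / 12.4 = 0.42).

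**3. False positives.** Over all allocations, the unadjusted test rejected a true null in 4.6-5.6% of simulated trials. Given a shift of 0.30 SE, the chance is P(Z > 1.66) + P(Z < −2.26) = 0.048 + 0.012 = 0.060. Simulation restricted to trials with an imbalance of 15 points or more agrees:

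| Per arm | Unadjusted | Adjusted |
|---|---|---|
| 20 | 5.7% | 4.8% |
| 30 | 6.4% | 5.5% |
| 50 | 7.0% | 5.0% |

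A harsher case takes 100 patients in total and two binary factors, each with an odds ratio of 3. Among the 4.4% of trials whose summed imbalance reached 30 points, the unadjusted test rejected 11.2% and a stratified test 3.5%.

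**4. Precision.** Simulated SE of the risk difference (20,000 replicates), crude v linear-model-adjusted, with gain = (crude / adjusted)² − 1:

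| Per arm | Crude | Adjusted | Gain |
|---|---|---|---|
| 20 | 0.153 | 0.147 | 8% |
| 30 | 0.124 | 0.118 | 10% |
| 50 | 0.096 | 0.091 | 11% |

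The crude column agrees with the formula in step 2 to within 0.002. Independent repeats put the gain between 7% and 13% over this range of sizes. The standardised estimate proposed below targets the same risk difference; these figures are for the linear-model version.

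**5. Power.** With an assumed treatment odds ratio of 0.4, power rises from 20.8% to 21.2%, from 28.1% to 30.0% and from 44.5% to 47.7% at 20, 30 and 50 per arm. Over-stratifying can undo this. At 40 patients in total, with prognostic odds ratios of 3, a four-stratum Mantel-Haenszel test had 20.5% power against 21.2% unadjusted.

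**The case against.** The planned test is valid. Under randomisation, chance imbalance is part of the variation that the p-value already allows for, and the overall error rate stays near 5%. A reader might infer from the mixed population that the primary result is biased or cannot be interpreted. The documents do not support that: the effect is conditional on an imbalance occurring and, on the figures above, would rarely change the conclusion. This objection stands, and it limits the point to a refinement.

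Three other strong readings also fail.
- **That aetiology is already in hand as a variable for every patient.** LVEF is; aetiology is not. The plan records coronary disease, infarction and revascularisation history, angiography is selective, and qualifying scar may first be shown on the electroanatomic map, during the procedure and so after allocation. A definition is needed before the factor can be used.
- **That section K assigns chi-square to the primary endpoint.** It assigns no test. The reading follows from treating recurrence as categorical, and Fisher's exact test is equally available.
- **That aetiology and LVEF are known strong predictors here.** Nothing in the documents gives their effect on recurrence after ablation. The 26% v 50% and 0.6 per SD are assumptions.

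It is also fair to say that covariate choice in a sample of unknown size is a judgement. Naming only two covariates in advance, and keeping the unadjusted result alongside, largely answers this.

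**Conclusion.** The point holds as a worthwhile, low-cost improvement and not as a flaw in validity. What is certain from the text is that eligibility is mixed, no stratification is stated, only unadjusted tests are listed, and LVEF is measured in everyone at baseline but not used in the comparison. The size is uncertain. Under the assumed prognostic effects, adjustment is worth roughly 7-13% more patients at 20-50 per arm, and it removes a shift of about 0.3 SE when a 15-point aetiology imbalance arises at 30 per arm. Weaker prognostic effects would shrink both figures, and a larger trial would make such imbalances rarer. Confidence in the absence of adjustment is high; confidence in the magnitude is moderate.

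**What to change.** In section K, name one primary analysis of VT recurrence: a standardised (covariate-adjusted) risk difference. Fit one logistic model with arm and two baseline covariates, average the predicted risks over all randomised patients under each arm, and report the difference with a 95% confidence interval. The covariates are:

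1. LVEF, continuous, by Simpson's method (item E).
2. Ischaemic v non-ischaemic status, with the rule written down before analysis. Derive it from the coronary disease, infarction and revascularisation history recorded before randomisation (item A4), and not from procedural mapping.

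Report the unadjusted chi-square or Fisher's exact result as supportive. State the time window to which the recurrence risk refers, because section J gives only an average follow-up of 12 months.

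The cost is a paragraph of SAP text, one written definition and one model on baseline data that the plan already collects. The downside is a modelling step in a probably small sample, so the list should stop at these two covariates. If allocation is complete, stratified randomisation is no longer possible and adjustment is the remaining remedy. If outcomes by arm have already been examined, the adjusted analysis should be labelled post hoc.

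### Allocation is made before the voltage map and late-potential tagging that both arms share, and no masking of the mapper is described, so knowledge of the arm could affect the tags from which ablation targets are drawn

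*Combined protocol and SAP*

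**What the plan says.** Section G (Randomization) places allocation ahead of the procedure: "Patients were randomly allocated to either DEEP group or non-DEEP group before the procedure". It adds: "Patients were informed of the group to which they have been randomized". It says nothing about when the operator or mapper learns the group.

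Section I (Mapping and Ablation Strategy) then describes a step common to both arms: "All patients underwent bipolar voltage mapping during sinus rhythm. Mapping was performed by either an irrigated tip ablation catheter" (four such catheters are named) "or a multi-electrode mapping catheter" (one is named). LPs, defined by signal character and by timing relative to the QRS, "were pinpointed and tagged".

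The arms separate only after this, in the same section: "Patients allocated to the DEEP group were subjected to further analysis of their LPs by RV extrastimulus pacing". The test is numeric: "If the difference between the 2 measured values was > 10 ms, the analyzed LP was annotated as a DEEP". Multicomponent signals have their own criterion, splitting by more than 10 ms after S2. Ablation is at first confined to DEEP points in the DEEP arm, and is directed at every LP in the non-DEEP arm. Section I also states: "The percentage of points with LPs and DEEPs was calculated in relation to the total number of mapped points".

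Section J (Follow up) makes VT recurrence the primary endpoint.

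**The concern.** The shared map supplies the raw material for both strategies. If it is made by someone who knows the arm, it may not be made in the same way in both arms.

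The same tag has different consequences. In the non-DEEP arm, an LP tag adds a site to ablate. In the DEEP arm, it adds a site to test, and the site becomes an initial target only if it responds to S2. An operator who knows which applies could, without intending to, map more or less densely or treat borderline signals differently.

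What is at stake is attribution. The trial asks whether choosing targets by the DEEP rule changes VT recurrence. If mapping also differed by arm, part of any difference in recurrence could come from the mapping. Nothing in the described workflow requires the arm to be known before pacing starts, so this exposure is avoidable.

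**Working it through.** No arithmetic tests this point, because the plan gives no figure for it. The check is to put the steps in order and see where the arm could matter.

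| Step | Section | Arms treated alike by the plan? | Arm already allocated? |
|---|---|---|---|
| Allocation; patients told | G | – | yes, from here on |
| Sinus-rhythm voltage map | I | yes | yes |
| LP tagging | I | yes | yes |
| RV extrastimulus pacing of LPs | I | no, DEEP arm only | yes |
| Initial ablation | I | no | yes |
| Further mapping and ablation if VT is still inducible | I | yes, by the same rule | yes |

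Two steps are common to both arms, precede the point where the arms diverge, and yet follow allocation: the voltage map and LP tagging.

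**Is the mapper masked?** Sections A to K mention no masking of the operator or mapper, no independent or core-laboratory reading, and no saving of the map before the arm is revealed.

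**Is there room for judgement?** The LP definition is explicit, but it sets no numeric threshold for amplitude, delay or duration. Map density is not specified. Section I names 4 + 1 = 5 mapping catheters without a selection rule. All 4 ablation catheters are among them, which leaves 5 − 4 = 1 that is used for mapping only. This describes the device list; it does not measure bias.

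**How do tags become targets?**
- Non-DEEP arm: each tagged LP is directly a target.
- DEEP arm: each tagged LP is a candidate. The interval is measured twice (drive train and S2), and the site is an initial target if the change exceeds 10 ms. A multicomponent signal qualifies by splitting of more than 10 ms. The 10 ms rule is numeric, but it is applied to signals found during mapping, so it does not remove the dependence on the map.

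**What does this mean for the LP percentage?** LP percentage = 100 × (points with LPs) / (mapped points). Both terms arise after allocation, so a difference between arms could reflect the substrate, the mapping, or both.

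The documents give no rate of tagging disagreement, no point counts and no recurrence rates by arm, so no estimate of bias can be computed.

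**The case against.** The strongest reply is that the key link is inferred. The plan says that patients were told their group; it does not say that the mapper knew it while tagging, and it shows no influence on the map. That is correct, and it limits the point to a risk that the design leaves open.

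Several narrower replies also stand:
- LP tagging is not free of criteria. A definition is given with a cited source; only a numeric threshold is absent.
- In the DEEP arm the path from tag to target is looser than in the non-DEEP arm. Multicomponent signals have a separate route, and it is not clear that each must first be tagged as an LP.
- Nothing links catheter choice to arm.
- The plan nowhere presents the LP percentage as a baseline characteristic, and it is not an endpoint. The caution concerns how it should be read when reported.
- The remedy reaches only the shared map. Pacing, lesion delivery, inducibility testing and later mapping remain open to the operator. Recurrence in patients without a defibrillator is ascertained by history from patients who know their group, which is a separate and more direct open-label route to the primary endpoint.

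None of this shows that the shared step is protected. That operators cannot be masked from pacing onward is no reason to leave the earlier step exposed. The recruitment dates and past tense suggest that allocation may be complete, but the document is dated before recruitment began, so the design change is still a proper first recommendation.

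**Conclusion.** The concern holds in a limited form. The shared map and LP tags are produced after allocation, without described masking, and with some discretion. They supply the direct targets in one arm and the candidates in the other. A difference in VT recurrence could therefore partly reflect mapping rather than the DEEP rule. Size and direction are unknown.

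This rests on two assumptions: that the operator could have known the arm during mapping, on which the documents are silent, and that mapping and tagging were finished before DEEP testing, as the order of Section I implies.

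A reader might go further and infer that mapping was in fact biased, or that the randomised comparison is invalid. The documents support neither. They contain no evidence that mapping differed by arm, and pre-procedure allocation leaves a valid comparison of the two strategies as delivered, mapping included. What is weakened is the attribution of a difference to the DEEP rule alone. The change is worth making; it is not a condition for the trial to be interpretable.

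**What to change.** **If allocation can still be changed.** Amend Section G so that the allocation is opened in the laboratory, by sealed or online means, only after the voltage map and LP tags are complete and saved, immediately before RV extrastimulus pacing. Tell patients their group after the procedure. The inclusion criteria accept scar evidence from an electroanatomic map; where that is the index map, confirm scar before the allocation is opened.

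**Cost.** Protocol wording and an in-laboratory allocation mechanism. Patients learn their group later than now planned. The operator must finish and save the tags first and, if DEEP testing was in practice done point by point during mapping, may have to return to LP sites. Only the shared map is protected.

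**If allocation is already complete.** Keep all patients as randomised in the primary analysis. State when the operator learned the arm. Report mapping catheter, number of mapped points and LP counts by arm, labelled as post-allocation measures, and give the LP percentage with its numerator and denominator. This costs reporting effort only, provided the map data were kept. It lets a reader see whether mapping differed between arms, but it cannot remove the effect of a difference.

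### Patients are told their arm although they could be kept unaware without a sham; without an ICD, this leaves an avoidable, probably small, risk of differential reporting of VT recurrence

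*Combined protocol and SAP*

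**What the plan says.** **Disclosure.** Section G (Randomization) allocates patients before the procedure and adds "Patients were informed of the group to which they have been randomized". No reason is given.

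**What the arms share.** Section H (Procedure) states "The electrophysiological study and ablation was conducted under general anesthesia under supervision of an anesthesiologist", with no distinction by arm. Under section I, every patient has voltage mapping in sinus rhythm, and both arms are ablated.

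**What differs.** Section I describes two differences, both within the procedure. One is added pacing: "Patients allocated to the DEEP group were subjected to further analysis of their LPs by RV extrastimulus pacing". The other is the ablation target. In the DEEP group, "ablation was initially restricted to points with DEEPs, while in the non-DEEP group, ablation aimed at elimination of all LPs".

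**How the primary endpoint is found.** Section J (Follow up) names VT recurrence as primary. Patients with an implanted defibrillator are followed by device interrogation. The others are followed by asking about symptoms or emergency admissions put down to VT. The section does not say at what time the presence of a defibrillator is judged.

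**Who may enter without an ICD.** The inclusion criteria accept "Sustained monomorphic VT documented by 12-lead electrocardiogram (ECG) or implantable cardioverter defibrillator (ICD) electrograms", so an ICD is not required.

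**Analysis.** Section K compares categorical variables by chi-square or Fisher's exact test. It plans no analysis by ICD status.

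**The concern.** When an endpoint depends partly on what patients say, and patients know their arm, reporting can differ between arms for reasons other than the treatment effect. Here the exposure is limited to patients without an ICD. Within that subset, symptoms are more exposed than admissions, although attributing an admission to VT is still a judgement.

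Two features make the point worth raising. The exposure is avoidable, because nothing described outside the procedure would reveal the arm to a patient who was anaesthetised throughout it. It also falls on the primary endpoint, where device-detected and history-based events are pooled and no result is planned that sets the history-based part aside. All-cause mortality is not exposed to patient reporting.

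**Working it through.** The documents give no sample size, recurrence rate, share of patients without an ICD, or error rate for history taking. There is therefore no figure of the plan's own to reproduce. Everything below is illustration on assumed inputs.

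**Assumed inputs**
- s = share without an ICD: 0.10, 0.30 or 0.50
- p = true recurrence, the same in both arms: 0.40
- g = gap between arms in the sensitivity of history taking, or in the rate of wrongly attributed symptoms
- device interrogation misses nothing and is unaffected by knowledge of the arm

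**Spurious difference in observed recurrence, in percentage points**

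| Mechanism | Formula | g | s = 0.10 | s = 0.30 | s = 0.50 |
|---|---|---|---|---|---|
| Missed events | s × p × g | 0.05 | 0.2 | 0.6 | 1.0 |
| Missed events | s × p × g | 0.20 | 0.8 | 2.4 | 4.0 |
| Missed events, half caught equally by emergency admission | s × p × 0.5 × g | 0.05 | 0.1 | 0.3 | 0.5 |
| Same | s × p × 0.5 × g | 0.20 | 0.4 | 1.2 | 2.0 |
| Symptoms wrongly attributed to VT | s × (1 − p) × g | 0.05 | 0.3 | 0.9 | 1.5 |

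For example, 0.30 × 0.40 × 0.20 = 0.024, or 2.4 points. Missed events span about 0.1 to 4 points. Wrong attribution is a separate term that adds or offsets according to its direction.

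**Effect on the test.** A wider grid was also run: p 20% to 40%, s 10% to 50%, g 10 to 30 points, missed events only. Sensitivity was 90% in the better-reporting arm and the two-sided level was 0.05, both assumed. The spurious difference ranges from 0.2 to 6.0 points. False-positive rates by the normal approximation, at assumed sizes of 30, 50 and 100 per arm:
- middle case (p 30%, s 30%, g 20 points; 1.8 points): 0.053, 0.055, 0.059
- extreme case (p 40%, s 50%, g 30 points; 6.0 points): 0.077, 0.096, 0.144

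**What an ICD-only result costs in precision.** With the same event rate and allocation ratio in ICD patients, the standard error relative to all patients is 1/√(1 − s) = 1.054, 1.195 or 1.414. That is 5%, 20% or 41% larger.

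**Whether comparing ICD with non-ICD patients could detect the bias.** With p = 0.40, the spurious gap inside the non-ICD subset is p × g = 2 points (g = 0.05) to 8 points (g = 0.20). The variance term is 2 × 0.40 × 0.60 = 0.48. With 30% non-ICD:
- 50 per arm (15 non-ICD, 35 ICD): standard error of the contrast = √(0.48/15 + 0.48/35) = 0.214, about 21 points
- 100 per arm (30 and 70): √(0.48/30 + 0.48/70) = 0.151, about 15 points

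Power to detect even 8 points at the two-sided 5% level is about 7% and 8% respectively, barely above the false-positive rate.

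**The case against.** The best case against the point is that it is small and only partly curable.

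- **Size.** Every input is assumed, and the effect is slight over most of the range. Larger values need many patients without an ICD together with a strong reporting gap, and the documents support neither. This stands, and it is why the point is minor.
- **Mechanism.** Both arms receive active ablation, and nothing suggests that patients were led to expect one target strategy to do better. This stands as a reason to expect a small effect. It does not make the effect zero, and an unknown direction cannot be taken as conservative.
- **The bigger gap may lie elsewhere.** Outside device follow-up, an event depends on someone attributing symptoms or an admission to VT. Masked assessment and ECG confirmation are not mentioned. This stands: keeping patients unaware leaves that judgement untouched. It is no reason to keep a separate exposure that can be avoided.
- **An analysis by ICD status as a diagnostic.** A reader might infer that comparing ICD with non-ICD patients would reveal any reporting bias. It would not. Power is very low, and a visible contrast could equally reflect different patients or different detection methods.
- **Timing.** The document is dated 28 September 2021, before the recruitment start implied by "Patient recruitment period was from October 2021 till January 2023", yet it is written largely in the past tense. If patients have already been told, masking is no longer possible, so the remedy has to cover both cases.

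**Conclusion.** The point holds in a limited form. The plan discloses allocation where it need not, and in patients without an ICD this creates an avoidable risk of differential reporting in part of the primary endpoint. Its direction is unknown. Its size is probably small: about 0.1 to 4 points from missed events, assuming 40% recurrence, 10% to 50% of patients without an ICD and a 5- to 20-point sensitivity gap. Because the documents give neither the recurrence rate nor the share without an ICD, even the word small rests on assumption.

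A reader might go further and infer that the VT recurrence comparison is biased, or that it favours one arm. The documents do not support that. They show a route for bias but no evidence that reporting differed, no stated expectation in favour of either arm, and objective follow-up for patients with a device.

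**What to change.** **If patients have not yet been told**, replace the disclosure sentence in section G with:

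> Patients consent to randomisation between two ablation-target strategies and are not told their allocation until follow-up is complete, unless they ask or it is needed for care.

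Take the follow-up history with the same fixed questions in both arms.

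**In either case**, add to section K:

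> The between-arm comparison of device-detected VT recurrence in patients with an ICD at randomisation is reported as a sensitivity analysis beside the overall result.

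Present this as an estimate little exposed to patient reporting, not as a test for bias. Defining the group at randomisation avoids sorting patients by an implant received later. The information should be obtainable from existing steps: the admission history covers "Previous episodes of ventricular tachycardia, requirement for external shock, ICD shocks", and section H records that "ICD therapies were inactivated" for the procedure.

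**Cost.** One protocol sentence, consent wording, a fixed question list and one extra table, with no sham and no added procedure. Discharge letters and follow-up staff must also avoid revealing the arm throughout follow-up, which section J puts at a mean of 12 months.

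**Limits.** Masking is partial, because the arm is disclosed on request or when care needs it. The ICD-only result is less precise and covers a different population. Attribution of non-ICD events by unmasked assessors is not solved.
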